6.0 Research questions

1. Is the NeoSpot a feasible, acceptable, and easy to use device when used by CHWs during community ANC outreach activities?
2. Can photoplethysmograph (PPG) sensor data from NeoSpot be used to develop an accurate and reliable blood pressure algorithm?

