7.0 Specific Aims

Aim 1: To describe the feasibility, acceptability, ease of use, and perceived confidence of pregnant women and CHWs to use the NeoSpot device during community ANC outreach

The novel test device, NeoSpot will be used by 12 CHWs during community ANC outreach activities to measure vital signs among pregnant women in Lusaka, Zambia. Through in-depth interviews (IDIs), we will determine and feasibility, acceptability, and ease of use, including design feedback, of the device by 12 CHWs and 12 pregnant women.

Aim 2: To obtain raw PPG data from the prototype NeoSpot device which will be used in the development of an accurate and reliable blood pressure algorithm.

During community ANC outreach activities, CHWs will take readings with the NeoSpot device from 125 pregnant women. The raw PPG sensor data will be used to train an autonomous machine learning model to extract arterial blood pressure systolic and diastolic values.

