8.0 Methodology

[figure not shown]
[figure not shown]
Study Design

The proposed study is a pilot feasibility trial to be implemented at Kanyama 1st Level Hospital and its wider catchment area among a prospective cohort of pregnant women during community ANC outreach activities. The test device, NeoSpot, will be used by CHWs and will monitor vital signs and blood pressure in each participant.

The neoSpot™ device is a 5-in-1 wearable vital signs monitor designed to measure temperature, pulse rate (PR), respiratory rate (RR), blood oxygen saturation (SpO₂) and blood pressure. It is currently under the final stages of development by Neopenda, PBC (Chicago, IL, USA) under international medical device standards and for feasibility in low-resource settings, including:

low-power design, safe re-usability, ruggedness, portability, and ease of use. The device weighs approximately 15 grams and measures 42 x 36 x 14 mm. It contains two non-invasive sensors: an optical reflectance pulse oximeter and a digital temperature sensor. These sensors measure signals from the surface of the patient's skin, and algorithms within the device calculate the pulse rate, respiratory rate, SpO₂, blood pressure and temperature. The device will be synced with a smartphone, which will be provided to the CHWs by the study.

The device is made of medical grade polyetherimide plastic and can be worn through an adjustable band. The bands are made of medical-grade silicone rubber. The devices are wireless and powered by medically-certified rechargeable batteries. The pulse rate, respiratory rate, temperature, blood pressure and oxygen saturation data are recorded and transmitted to an app on a smart phone. Upon final validation and field testing, Neopenda will pursue CE mark certification for the neoSpotTM technology.

Study site and settings

We propose that this prospective pilot feasibility study take place at the Kaynama 1st Level Hospital wider catchment area in Lusaka, Zambia. The area records around 10,000 deliveries a year, therefore, we are confident that we will screen 125 pregnant women in our stated period.

Study Population

Aim #1

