Study participants for the qualitative aim of the study will be comprised of 12 Community Health Workers (CHWs) who have used the NeoSpot device during routine government community ANC outreach activities. All 12 CHWs who consent will undergo in-depth interviews (IDIs) in addition to 12 pregnant women who have consented to participate in Aim #2 of the study (below). Study participants meeting the following inclusion and exclusion criteria will be enrolled:

Inclusion criteria

1. CHWs who have used the NeoSpot device, or
2. Pregnant women who have experienced the device under Aim #2
2. 18+ years of age
3. Willing to consent

Exclusion criteria

1. Pregnant women not enrolled under Aim #2 below
2. Unable to consent

Aim #2

Study participants will be pregnant women recruited during the community ANC outreach (n=125) on the following inclusion and exclusion criteria:

Inclusion criteria

1. Pregnant
2. 18+ years of age
3. Willing to consent

Exclusion criteria

1. Unable to consent
2. Not pregnant
3. Age below 18 years

Sample Size

Aim #1: For the qualitative aim of this pilot study, 12 CHWs who have used the NeoSpot device and 12 pregnant women who have been enrolled into the study under Aim #2 (below) will be approached and, if consented, enrolled into the study. A total of 24 IDIs will be conducted among the target population. The sample size may be increased if saturation is not reached using this sample size.

Aim #2: Twelve CHWs will be trained in the use of the NeoSpot and given the device to use during outreach activities. Potential study participants (i.e., pregnant women) will be approached

during the community ANC outreach activities. If interested, study staff will then discuss the study procedures, risks, and benefits in detail in Nyanja, Bemba, or English based on the study participant's preference. Should they be interested in the study, they will be consented. Following enrollment, the CHWs will measure the pregnant woman's vital signs and her blood pressure. A total of 125 study participants will be enrolled.

Study Procedures

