Study hired Research Assistants (RAs) will approach potential study participants for both study aims and consent them for study participation. Following enrollment, for Aim #1, CHWs and pregnant women will undergo IDIs in a safe and secure location. IDIs will last approximately 1 hour and they will be conducted in the preferred language of the consented study participant. All study participants will exit the study following the IDI. For Aim #2, study staff will measure their vital signs and blood pressure using the NeoSpot, which data will be automatically stored into the smartphone provided by the study. Results of the vital signs and the blood pressure will also be shared with the clinical treatment team following screening. The treating clinicians will notify the patient of the results and, if required, refer the pregnant women for appropriate care according to local standard of care. All study participants under Aim #2 will exit the study following this stage.

Data Collection

All data for Aim #1 will be recorded on a study audio recorder and then translated and transcribed onto a word document by a study team member. Once it is transcribed and has been reviewed for completeness, the audio recording will be destroyed.

For Aim #2, PPG data will be automatically collected and stored by the NeoSpot directly into the smartphone, without the use of data collection tools. It will be stored on smartphones provided to the CHWs by the study. Following data storage, PPG data will be used to develop an accurate and reliable blood pressure algorithm for future piloting. Confidentiality of patient identifiers will be protected by using a patient identification key that will be stored separately from the data set. Each study participant will be assigned a unique study identification number. The database will be password protected, accessible only to the study PI and data analyst.

Data Analysis

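### The plan conflicts on who takes the NeoSpot readings, and it judges feasibility from interviews alone, so no rate of usable readings by CHWs would be reported

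*Combined protocol and SAP*

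**What the plan says.** Section 6.0 asks: "Is the NeoSpot a feasible, acceptable, and easy to use device when used by CHWs during community ANC outreach activities". Section 4.0 describes the study as a feasibility trial meant to demonstrate feasibility and acceptability in CHW hands.

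**Who operates the device**
- Section 7.0, Aim 2: "CHWs will take readings with the NeoSpot device from 125 pregnant women".
- Section 8.0, Study Design: "The test device, NeoSpot, will be used by CHWs and will monitor vital signs and blood pressure in each participant".
- Section 8.0, Sample Size, Aim #2: "Following enrollment, the CHWs will measure" the woman's vital signs and blood pressure. The same paragraph has study staff explaining the study beforehand, so it treats the two groups as distinct.
- Section 8.0, Study Procedures, Aim #2: "study staff will measure their vital signs and blood pressure using the NeoSpot".

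**How feasibility is judged**
- Section 7.0, Aim 1: "Through in-depth interviews (IDIs), we will determine and feasibility, acceptability, and ease of use", from 12 CHWs and 12 pregnant women.
- Section 8.0, Data Analysis: thematic analysis for Aim #1. For Aim #2, the PPG data go to algorithm development and no other analysis is named.

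**What is captured**
- Section 8.0, Study Design: each vital-sign parameter, including blood pressure, is recorded and sent to the phone app.
- Section 8.0, Data Collection: "PPG data will be automatically collected and stored by the NeoSpot directly into the smartphone, without the use of data collection tools". It adds: "Each study participant will be assigned a unique study identification number".

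**What would be concluded**
- Section 3.0 says that a finding of feasibility and acceptability would be enough evidence to support using the device for vital signs and blood pressure in pregnant women.

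**The concern.** The research question is about one kind of user. A site works from the procedures text, and that is the one place that names a different user. If it is followed as written, the 125 readings show what study staff can do with the device, not what CHWs can do.

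The second issue is what counts as evidence of feasibility. Whether a CHW at an outreach session gets a usable reading, and how often, is a frequency. Twenty-four interviews (more if saturation is not reached) can describe difficulties but cannot give that frequency: only 12 of the 125 women are planned for interview, and they are chosen purposively. At stake is a positive feasibility conclusion, to be cited in support of using the device, with no figure behind it for how often a reading was obtained.

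**Working it through.** **Step 1: the operator.** Three places name CHWs (Aim 2 in section 7.0; Study Design and Sample Size in section 8.0). One names study staff (Study Procedures). Sample Size separates the two groups, and Study Procedures itself gives recruitment and consent to hired research assistants. Against that, the 12 CHWs are the people trained and given the device, and the phones that hold the data are theirs. Loose wording is therefore plausible, but the text does not settle it.

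**Step 2: the feasibility measure.** I looked through sections 3.0, 4.0 and 6.0 to 9.0 for a definition of a usable reading, a count of attempts, failures or repeats, a completion rate or a threshold. None appears in the visible text. The only arithmetic the plan offers here is 12 + 12 = 24 interviews, which agrees. There is no stated rate, power or precision to reproduce.

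**Step 3: what the planned sample could give.** Inputs from the documents: 125 women, 12 CHWs. Assumed, because the documents give no values: 112 women with a usable reading, and an intraclass correlation (ICC) by operator of 0.05, 0.10 or 0.20.

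- Estimate: 112/125 = 89.6%.
- Ignoring operators, the exact (Clopper-Pearson) 95% interval is 82.9-94.3%.
- Mean women per operator: m = 125/12 = 10.42.
- Design effect: DE = 1 + (m - 1) × ICC. Effective sample size: 125/DE.
- Korn-Graubard adjustment for having only 12 operators: multiply the effective size by (t(0.975, 124)/t(0.975, 11))² = (1.979/2.201)² = 0.809 to get n*. Then apply the exact interval to 0.896 × n* successes out of n*.

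| ICC (assumed) | DE | 125/DE | n* | 95% interval | Estimate minus lower limit |
|---|---|---|---|---|---|
| 0.05 | 1.47 | 85.0 | 68.7 | 79.9-95.7% | 9.7 points |
| 0.10 | 1.94 | 64.4 | 52.1 | 78.0-96.3% | 11.6 points |
| 0.20 | 2.88 | 43.4 | 35.1 | 74.6-97.3% | 15.0 points |

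The intervals are asymmetric, so a single half-width would understate the downside. The lower limit lies about 10 to 15 points below the estimate once operators are allowed for, against 6.7 points (89.6 - 82.9) if they are ignored. At other assumed results, the intervals ignoring operators are 89.8-98.2% for 119/125 and 71.9-86.6% for 100/125. At ICC 0.10 they become 85.4-99.2% and 66.6-89.8%.

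**The case against.** The strongest reply is that Aim 1 is a coherent qualitative design. It is worded as a description, it names an analysis framework in which feasibility is a domain, and it promises no rate. That stands as far as it goes: the interviews are sound for acceptability, ease of use and perceived confidence, and the CHWs who consent can report failures they met.

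A reader might infer from the operator conflict that the first research question cannot be answered at all. The documents do not support that. As planned, the question rests on interviews, and the Aim #1 study population is limited to CHWs who have used the device during routine outreach. The conflict damages the 125 readings as evidence of CHW use; it does not by itself undo the interviews. It could, however, leave open where those CHWs gained their experience.

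A reader might also infer that the data for a rate are not being collected. That too goes further than the text. Every parameter and the PPG signal are stored automatically and each woman has a study number, so much of the count may need no new form. What is unstated is whether the app keeps failed or repeated attempts and who held the device.

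Two further points stand. The sentence in section 3.0 is part of a rationale and is not a decision rule; section 8.0 still places final validation and field testing before certification. And two figures are not shown and one passage was removed, so the absence of a planned rate can be asserted only for the visible text.

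**Conclusion.** Both parts hold in a limited form. The operator wording conflicts and must be reconciled; it may prove to be no more than a slip. The visible plan judges feasibility by interview only and would report no frequency of usable readings, although most of the data needed are already to be stored.

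The numerical size is illustrative. At an assumed 89.6% usable, 125 women and 12 operators would put the lower 95% limit somewhere between 79.9% and 74.6% for ICCs of 0.05 to 0.20. That is a useful description, but no test against a standard, since the plan sets none. The rate and the ICCs are assumptions, and the calculation takes operator workloads as roughly equal.

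On blood pressure, the conclusion in section 3.0 goes beyond anything this study can show. Section 1.1 puts that measurement at an early stage, Data Analysis leaves the algorithm to be developed and piloted later, and a usable trace says nothing about accuracy.

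This should be corrected before enrolment, because the operator, and any attempts the app does not keep, cannot be recovered reliably afterwards.

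**What to change.** 1. **Study Procedures (8.0):** reconcile the operator with section 7.0 and with Study Design and Sample Size. Record the operator of each reading, and report any taken by study staff separately.
2. **Data Analysis (8.0), Aim #2:** define a usable reading before any trace is examined. From the stored data, report the number and proportion of the 125 enrolled women with a usable PPG trace and with each parameter obtained, with a 95% interval allowing for clustering by operator.
3. **Data Collection (8.0):** establish whether the app logs failed and repeated attempts. If it does not, add a one-line tally per woman against the existing study number, and amend the statement that no data collection tools are used.
4. **Section 3.0:** limit the conclusion to feasibility and acceptability of use, and remove the blood pressure claim.

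Optional: include some women with failed or repeated readings among the 12 interviewed, and count women approached and declining. The latter reflects uptake of a study that pays 100 ZMK and does not measure acceptability of the device.

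The cost is a little logging and analysis time, possible ethics review of the short tally, and perhaps a less favourable feasibility figure. No extra enrolment is needed.

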8.0 Methodology

[figure not shown]
[figure not shown]
Study Design

The proposed study is a pilot feasibility trial to be implemented at Kanyama 1st Level Hospital and its wider catchment area among a prospective cohort of pregnant women during community ANC outreach activities. The test device, NeoSpot, will be used by CHWs and will monitor vital signs and blood pressure in each participant.

The neoSpot™ device is a 5-in-1 wearable vital signs monitor designed to measure temperature, pulse rate (PR), respiratory rate (RR), blood oxygen saturation (SpO₂) and blood pressure. It is currently under the final stages of development by Neopenda, PBC (Chicago, IL, USA) under international medical device standards and for feasibility in low-resource settings, including:

low-power design, safe re-usability, ruggedness, portability, and ease of use. The device weighs approximately 15 grams and measures 42 x 36 x 14 mm. It contains two non-invasive sensors: an optical reflectance pulse oximeter and a digital temperature sensor. These sensors measure signals from the surface of the patient's skin, and algorithms within the device calculate the pulse rate, respiratory rate, SpO₂, blood pressure and temperature. The device will be synced with a smartphone, which will be provided to the CHWs by the study.

The device is made of medical grade polyetherimide plastic and can be worn through an adjustable band. The bands are made of medical-grade silicone rubber. The devices are wireless and powered by medically-certified rechargeable batteries. The pulse rate, respiratory rate, temperature, blood pressure and oxygen saturation data are recorded and transmitted to an app on a smart phone. Upon final validation and field testing, Neopenda will pursue CE mark certification for the neoSpotTM technology.

Study site and settings

We propose that this prospective pilot feasibility study take place at the Kaynama 1st Level Hospital wider catchment area in Lusaka, Zambia. The area records around 10,000 deliveries a year, therefore, we are confident that we will screen 125 pregnant women in our stated period.

Study Population

Aim #1

Study participants for the qualitative aim of the study will be comprised of 12 Community Health Workers (CHWs) who have used the NeoSpot device during routine government community ANC outreach activities. All 12 CHWs who consent will undergo in-depth interviews (IDIs) in addition to 12 pregnant women who have consented to participate in Aim #2 of the study (below). Study participants meeting the following inclusion and exclusion criteria will be enrolled:

Inclusion criteria

1. CHWs who have used the NeoSpot device, or
2. Pregnant women who have experienced the device under Aim #2
2. 18+ years of age
3. Willing to consent

Exclusion criteria

1. Pregnant women not enrolled under Aim #2 below
2. Unable to consent

Aim #2

Study participants will be pregnant women recruited during the community ANC outreach (n=125) on the following inclusion and exclusion criteria:

Inclusion criteria

1. Pregnant
2. 18+ years of age
3. Willing to consent

Exclusion criteria

1. Unable to consent
2. Not pregnant
3. Age below 18 years

Sample Size

Aim #1: For the qualitative aim of this pilot study, 12 CHWs who have used the NeoSpot device and 12 pregnant women who have been enrolled into the study under Aim #2 (below) will be approached and, if consented, enrolled into the study. A total of 24 IDIs will be conducted among the target population. The sample size may be increased if saturation is not reached using this sample size.

Aim #2: Twelve CHWs will be trained in the use of the NeoSpot and given the device to use during outreach activities. Potential study participants (i.e., pregnant women) will be approached

during the community ANC outreach activities. If interested, study staff will then discuss the study procedures, risks, and benefits in detail in Nyanja, Bemba, or English based on the study participant's preference. Should they be interested in the study, they will be consented. Following enrollment, the CHWs will measure the pregnant woman's vital signs and her blood pressure. A total of 125 study participants will be enrolled.

Study Procedures

Study hired Research Assistants (RAs) will approach potential study participants for both study aims and consent them for study participation. Following enrollment, for Aim #1, CHWs and pregnant women will undergo IDIs in a safe and secure location. IDIs will last approximately 1 hour and they will be conducted in the preferred language of the consented study participant. All study participants will exit the study following the IDI. For Aim #2, study staff will measure their vital signs and blood pressure using the NeoSpot, which data will be automatically stored into the smartphone provided by the study. Results of the vital signs and the blood pressure will also be shared with the clinical treatment team following screening. The treating clinicians will notify the patient of the results and, if required, refer the pregnant women for appropriate care according to local standard of care. All study participants under Aim #2 will exit the study following this stage.

Data Collection

All data for Aim #1 will be recorded on a study audio recorder and then translated and transcribed onto a word document by a study team member. Once it is transcribed and has been reviewed for completeness, the audio recording will be destroyed.

For Aim #2, PPG data will be automatically collected and stored by the NeoSpot directly into the smartphone, without the use of data collection tools. It will be stored on smartphones provided to the CHWs by the study. Following data storage, PPG data will be used to develop an accurate and reliable blood pressure algorithm for future piloting. Confidentiality of patient identifiers will be protected by using a patient identification key that will be stored separately from the data set. Each study participant will be assigned a unique study identification number. The database will be password protected, accessible only to the study PI and data analyst.

Data Analysis

Aim #1: We will conduct 24 IDIs with pregnant mothers (12) and CHWs (12) from the study sites. Sample size will be increased if thematic saturation is not reached. The study RA will conduct a total of 24 IDIs, among 12 purposively selected pregnant women from Aim #2 and 12 CHWs. IDIs will be audio-recorded, transcribed, and translated into English prior to thematic analysis using NVivo 9.0 (QSR International, Australia). We will conduct hybrid analysis using inductive reasoning to identify themes and deductive reasoning based on the suitability, feasibility and acceptability (SFA) framework.

Aim #2: PPG data will be extracted from the database and used to further develop a reliable and accurate blood pressure algorithm, which will be piloted in the near future.

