3.0 Rationale/Justification

Many novel interventions are introduced to LMICs with little-to-no evidence of their successful performance, applicability, effectiveness, and feasibility and acceptability by the providers. There is need for robust testing and evaluation of innovations to ensure that they serve their intended purposes before they are introduced into common practice. The justification for this study is the need to generate evidence of feasibility and acceptability for neoSpot™ on pregnant women, so as to inform any changes or considerations for its use in LMIC settings. This proposed study is unique, impactful, and scalable given the immediate clinical application by CHWs during community ANC visits.

If the NeoSpot device shows to be feasible and acceptable for use by CHWs and by pregnant women, there would be sufficient evidence to support the use of the device to measure vital signs and blood pressure among pregnant women. This study has the potential to improve access vital signs measurements during both community and clinic activities as it would increase identification and improve treatment of pregnant women with danger signs such as eclampsia/pre-eclampsia, fever, etc. in low-resource settings and would serve the larger aim of reducing maternal and neonatal morbidity and mortality.

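### Aim 1 judges feasibility and acceptability only from people who took up the device, and nothing in the plan records those who did not

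*Combined protocol and SAP*

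**What the plan says.** Section 7.0 makes in-depth interviews the means of answering Aim 1, and the Data Analysis part of section 8.0 lists no other data for it.

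Eligibility is set in section 8.0, Study Population, Aim #1. CHWs qualify as "CHWs who have used the NeoSpot device, or" and women as "Pregnant women who have experienced the device under Aim #2". The first exclusion criterion is "Pregnant women not enrolled under Aim #2 below".

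The Sample Size part gives the numbers. For Aim 1 it will approach "12 CHWs who have used the NeoSpot device and 12 pregnant women who have been enrolled into the study under Aim #2", and "A total of 24 IDIs will be conducted among the target population". For Aim 2, "Twelve CHWs will be trained in the use of the NeoSpot and given the device to use during outreach activities", and "A total of 125 study participants will be enrolled". Women are approached at outreach, and only those who are interested go on to consent. According to Data Analysis, the 12 women are chosen purposively; no selection criteria are stated.

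Section 3.0 states what a positive result would mean: "If the NeoSpot device shows to be feasible and acceptable for use by CHWs and by pregnant women, there would be sufficient evidence" to support using the device to measure vital signs and blood pressure in pregnant women.

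**The concern.** A feasibility study should be able to see non-uptake. If a CHW is trained and handed a device but never uses it at outreach, or a woman turns down the reading because of the device, that bears directly on whether the device can be deployed. Under the Aim 1 criteria neither person can be interviewed. The documents also describe no log that would show they existed: no count of women approached and declining, and none of devices issued against devices used.

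The interviews will therefore describe the experience of people who took the device up. That is a sound basis for ease of use and design feedback. It is a weaker basis for the broader statement in section 3.0, which speaks of CHWs and pregnant women without restriction. Refusals and non-use cannot be reconstructed once outreach has ended.

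**Working it through.** **Inputs from section 8.0.** 12 CHWs trained and given the device; 12 CHWs and 12 women interviewed; 24 interviews in total; 125 women enrolled under Aim 2. The documents give no refusal rate, no non-use rate and no success threshold for Aim 1.

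**1. The plan's own figure.** 12 + 12 = 24 interviews, as stated. The women interviewed are 12/125 = 9.6% of those enrolled.

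**2. Who can be heard under the criteria.**

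| Group | Eligible for Aim 1 interview? | Counted elsewhere in the plan? |
|---|---|---|
| CHW who used the device, with or without difficulty | Yes | Not applicable |
| CHW trained and issued a device, never used it | No | No |
| Woman enrolled and measured, whatever her opinion | Yes | Yes, among the 125 |
| Woman approached who declined Aim 2 | No, by explicit exclusion | No |

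The gap lies in the second and fourth rows.

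**3. CHWs.** Twelve are trained and twelve are to be interviewed. If all 12 use the device, the criterion removes 12 − 12 = 0. It matters only if a trained CHW does not use the device. If non-users were replaced to reach 12 users, 13 trained would mean 12/13 = 92.3% use and 15 trained would mean 12/15 = 80.0%. Nothing in the plan would report either figure.

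**4. Women, with assumed acceptance shares.** Let a be the share of approached women who enrol. Number approached = 125/a, rounded up; decliners = number approached − 125. The last column supposes that all 12 interviewed women are favourable, that all enrolled women are too, and that every refusal is due to the device. It is therefore a worst case, equal to a × 1.

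| Assumed a | Approached | Unrecorded decliners | Worst-case favourable share among all approached |
|---|---|---|---|
| 100% | 125 | 0 | 100% |
| 90% | 139 | 14 | 90% |
| 80% | 157 | 32 | 80% |
| 70% | 179 | 54 | 70% |
| 50% | 250 | 125 | 50% |

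The interview results would look the same in every row. These figures count refusals for any reason; they do not measure bias.

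**5. Can dissatisfaction among users still appear?** Yes. If 20% of enrolled women were dissatisfied, the chance that 12 chosen at random were all favourable would be 0.8^12 = 0.069; at 10% it would be 0.9^12 = 0.282. Selection is purposive, so this only illustrates that the interviews are not closed to negative views.

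**The case against.** A reader might infer that the criteria shut out everyone for whom the device was not feasible or acceptable. They do not. They ask for use or experience, not for success, satisfaction or a valid reading. A CHW who tried the device and struggled, or a woman who was measured and disliked it, remains eligible, and purposive selection could even seek such people out. This objection stands.

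Three further objections carry weight:

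- **The CHW criterion is close to empty as planned.** The trained group and the interviewed group are the same 12 people unless someone does not use the device. A CHW might also miss outreach through illness or scheduling, so non-use is not always a mark against the device. Both points stand.
- **Declining the study is not rejecting the device.** Women decide before it is applied and may refuse for lack of time, for privacy or from reluctance about research. The 100 ZMK payment in section 9.0 works in the other direction, since a woman may consent without finding the device acceptable. This stands, and it means that an acceptance proportion is not a direct measure of device acceptability.
- **Aim 1 is descriptive and thematic.** It estimates no proportion and has no pass mark, and interviewing people with experience is the right choice for ease of use and design feedback. This also stands.

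None of this makes non-uptake visible, and none of it supports the reach of the conclusion in section 3.0.

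**Conclusion.** The point holds in a limited form. The Aim 1 criteria bar non-using CHWs and declining women from interview, and the documents plan no count of either group. Where non-uptake is due to the device, the findings lean favourable; where it has other causes, they need not.

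The size of any bias cannot be computed, because refusal and non-use rates are not given. The refusal counts shown rest on assumed rates. For CHWs the effect is nil if all 12 use the device.

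The study is not invalidated, and the user interviews remain useful for what they can show. The defect is that section 3.0 draws a general conclusion from users alone, with no uptake figures beside it.

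**What to change.** 1. In section 8.0, Study Population, Aim #1, change the CHW criterion to: CHWs trained and issued with a NeoSpot for this study, whether or not they used it. Invite all 12 on that basis.
2. Have the research assistants, who already approach potential participants under Study Procedures, keep an anonymous tally of women approached for Aim 2, women who declined, and a short reason (device, time, privacy, other). Define what counts as an approach, so that the denominator is fixed. Record devices issued against devices used.
3. Report overall uptake and device-related refusals separately, beside the interview themes. Present them as feasibility measures and not as a direct measure of device acceptability.
4. Limit the section 3.0 conclusion to people who used or experienced the device, read together with those uptake figures.
5. Keep the user interviews as planned for ease of use and design feedback, and state the criteria for the purposive choice of the 12 women.

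Reconcile one related inconsistency at the same time. Sample Size, Aim #2 has CHWs take the readings, while Study Procedures assigns them to study staff. This decides who counts as having used the device.

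The cost is one reworded eligibility line, a tally sheet, a narrower sentence in section 3.0 and a few seconds per approach. No extra participants or staff are needed. The result may be less favourable.
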